2.5 Risks of combining Diamyd[®] and etanercept and vitamin D supplemenetation

We would not foresee that the addition of an anti-inflammatory treatment to the Diamyd[®] treatment would increase the theoretical risks of Diamyd[®], such as acceleration of the autoimmune process, undesirable effects on the immune system, or neurological disease. We also do not believe that the risks of anti-TNF α therapy, which are mostly the side-effects of compromised immunity, should be increased by the presence of a native antigen. There are no anticipated risks supplementing with vitamin D in the proposed doses.

2.6 Justification

We argue that etanercept (Enbrel), Diamyd and vitamin D in the proposed doses, and with the proposed exclusion and inclusion criteria, and careful safety plan and follow-up are justified to try to stop the devastating progress of autoimmune beta cell destruction in those recently diagnosed with T1D, aiming to preserve blood glucose control and endogenous insulin secretion and thereby significantly reduce both acute and long-term complication of the disease.

We propose that etanercept and Diamyd will synergize in a novel manner to produce extended beta cell function in those newly diagnosed with T1D.

As explained in the rational, we believe, that when etanercept therapy is added to GAD-alum treatment, GAD-specific autoantibody levels and effector T cell activity and number will be reduced while GAD-specific Treg number and function will be maintained. Due to its acute beta-cell-protective and metabolic effects, etanercept will also preserve beta cells directly. This will produce a deviation of the diabetes autoimmune response towards a regulatory phenotype of sufficient critical mass to lead to a significant and prolonged effect on beta cell preservation.

It is true that there is no documented pre-clinical data on the combination of etanercept and GAD immunotherapy in T1D. There are however positive results from the use of TNF α inhibitors in T1D models as well as positive clinical data on etanercept in both children and adults with T1D, suggesting that beta cell destruction can be arrested leading to better metabolic control (78-81). We do not expect the individual risks of GAD-alum and etanercept therapy to be increased by combining them.

There are no anticipated risks with the proposed vitamin D supplementation.

When summarizing the pros and cons, we argue that there is a clear possibility of therapeutic benefit of great importance whereas the adverse events and risks are reasonable as well as ethically and medically justified in the efforts to save residual insulin secretion at onset of T1D, as we know that T1D without residual insulin secretion is a dangerous disease in spite of very heavy and advanced treatment, during the whole life.

3 Aim of Present Study

Our primary aim of the present pilot study is to ensure the combination of etanercept, Vitamin D and GAD-alum is tolerable in children newly diagnosed with T1D. Secondly we want to study how this regimen influences the immune system, block TFN-alfa, and other dangerous cytokines but rather cause the desired Th-2 deviation, increase of T-regulatory cells, and hopefully preservation of residual beta cell function although we do not expect to show statistically convincing proof with this small pilot group of patients in an open trial.

A third aim is to receive more information on how GAD-alum could be combined with other types of treatment to improve efficacy without unacceptable non-justified risk of adverse events.

Thus we want to evaluate the tolerability of a combination therapy of GAD-alum, vitamin D in rather large dose and etanercept given in the same dose as used in the treatment of arthritis also in children.

Based on the results of this open pilot study we then want to use this knowledge for design of a larger Phase II trial to get more robust information. The main long-term goal is then to find a treatment at onset of T1D in young patients which is easy to administer at any clinical setting, tolerable for the patients, reasonably safe, and which can preserve residual insulin secretion and give the patients a better quality of life, with less acute complications and in the long run less risk of late complications.

4 **Objectives and Endpoints**

4.1 Objectives

- Evaluate the tolerability of a combination therapy with Diamyd, Vitamin D and etanercept
- Evaluate how the above mentioned treatments influence the immune system and endogenous insulin secretion

4.2 Endpoints

4.2.1 Primary endpoints

Primary endpoints:

To Evaluate the tolerability of a combination therapy with Diamyd, Vitamin D and etanercept at Month 6 (main study Period), 9, 15 and 30 (extension study period)

Variables to evaluate tolerability:

- Reactions of the injection site
- Infections
- Occurrence of Adverse Events (AEs)
- Occurrence of Serious Adverse Events
- Physiological and Neurology assessments
- Laboratory measurments (biochemistry and haematology), including Calcium and Vitamin D in serum
- GAD65AB titer (GADA)

4.2.2 Secondary endpoints

Secondary endpoints:

To evaluate how the above mentioned treatments influence the immune system and endogenous insulin secretion at at Month 6 (main study Period), 9, 15 and 30 (extension study period)

Variables to evaluate the influence on the immune system:

- Inflammatory markers, especially TNF-alfa, IL-1 beta, IL-2, IL-17
- Th2-deviation of cell-mediated immune response seen e.g. as increased ratio of IL-5,10, 13 in comparison with IFN-gamma, TNF-alfa, IL-1 beta and IL-17
- Increase of T-regulatory cells

Variables to evaluate the effect of endogenous insulin secretion:

- C-peptide (90 minute value and AUC_{mean 0-120 min}) during an MMTT
- Proportion of patients with a stimulated maximum C-peptide level above 0.2 nmol/L
- Fasting C-peptide
- Hemoglobin A1c (HbA1c)

• Exogenous insulin dose per kg body weight and 24 hours

5 **Population**

Consecutive patients with recent-onset T1D patients at Swedish pediatric clinics are given information about the study and they and their parents are asked to participate in the trial.

5.1 Inclusion Criteria

- 1. Informed consent given by patients and parent(s)/legal guardian(s)
- 2. Type 1 diabetes according to the ADA classification, diagnosed within the previous 100 days at the time of screening
- 3. Age 8.00 -17.99 years at time of screening
- 4. Fasting C-peptide at time of screening ≥ 0.12 nmol/L
- 5. Positive for GADA but < 50 000 Units
- 6. Menarchal females must agree to avoid pregnancy and have a negative urine pregnancy test
- 7. Immunity against Varicella, either through previous infection or vaccination
- 8. Patients must follow the Swedish vaccination programme
- 9. Patients of childbearing potential must agree to using adequate contraception, if sexually active, until 1 year after the last administration of GAD-alum and etanercept. Adequate contraception is as follows:

For females of childbearing potential:

- a. oral (except low-dose gestagen (lynestrenol and norestisteron), injectable, or implanted hormonal contraceptives (females)
- b. intrauterine device (females)
- c. intrauterine system (for example, progestin-releasing coil) (females)
- d. vasectomized male (with appropriate postvasectomy documentation of the absence of sperm in the ejaculate)

For males of childbearing potential:

a. Condom (male)

5.2 Exclusion Criteria

- 1. Previous or current treatment with immunosuppressant therapy (although topical or inhaled steroids are accepted)
- 2. Continuous treatment with anti-inflammatory drug (sporadic treatment e.g. because of headache or in connection with fever a few days will be accepted)
- 3. Treatment with any oral or injected anti-diabetic medications (especially hypoglycemic agents) other than insulin
- 4. Treatment with Vitamin D, marketed or not, or unwilling to abstain from such medication during the trial
- 5. A history of hypercalcemia
- 6. A history of anaemia or significantly abnormal haematology results at screening
- 7. A history of epilepsy, head trauma or cerebro-vascular accident, or clinical features of continuous motor unit activity in proximal muscles
- 8. Clinically significant history of acute reaction to vaccines or other drugs in the past
- 9. Treatment with any vaccine within 4 months prior to planned first administration of GAD-Alum or planned treatment with vaccine up to 4 months after the last injection with GAD-Alum, including influenza vaccine
- 10. Participation in other clinical trials with a new chemical entity within the previous 3 months
- 11. Inability or unwillingness to comply with the provisions of this protocol
- 12. A history of alcohol or drug abuse
- 13. A significant illness other than diabetes within 2 weeks prior to first dosing
- 14. Known human immunodeficiency virus (HIV)
- 15. Prior or active viral hepatitis B or C infection
- 16. Females who are lactating or pregnant (for females who have started menstruating the possibility of pregnancy must be excluded by urine βHCG on-site within 24 hours prior to the GAD-Alum and etanercept administration, respectively)
- 17. Males or females not willing to use adequate contraception, if sexually active, until 1 year after the last GAD-Alum and etanercept administration, respectively
- 18. Presence of associated serious disease or condition, including active skin infections that preclude subcutaneous injection, which in the opinion of the investigator makes the patient non-eligible for the study.
- 19. Deemed by the investigator not being able to follow instructions and/or follow the study protocol
- 20. Active infection, including chronic and local infection or a history of previous tendency to serious infections, recent or ongoing uncontrolled bacterial, viral, fungal or other opportunistic infections, or known infection with active EBV or CMV
- 21. Hypersensivity to the active substance in Enbrel (etanercept) or other ingredients in Enbrel
- 22. Active or inactive (latent) tuberculosis (TBC) at screening
- 23. History of malignancy or significant cardiovascular disease
- 24. Current or history of leukopenia, anemia and/or thrombocytopeni
- 25. Liver disease (clinical or hepatic enzymes >3 times the upper limit of normal (ULN))
- 26. Renal insufficiency (clinical or creatinine >3 times the upper limit of normal (ULN))
- 27. MS, undefined neurologic condition or known SLE, or anti-nuclear or known doublestranded DNA antibody positivity
- 28. Arrhythmia
- 29. Pancreatitis
- 30. Vitamin D serum levels >100 nmol/L at screening

5.3 Recruitment and Screening

Eligible subjects and their parent(s) / legal guardian(s) will have the study explained to them, and will receive the written patient information. After having had the time to review the nature of the study, they will have the opportunity to ask questions to the investigational team. If, after this, the subjects agree to participate, they will personally sign and date the written informed consent form. Patients and their parent(s)/legal guardian(s) will provide written informed consent before any study-related procedures are performed.

The patients and their parent(s)/legal guardian(s) will then receive a copy of the signed and dated patient information/informed consent form.

5.3.1 Screening for tuberculosis (exclusion criterion)

All patients will, at the screening visit, be screened for tuberculosis according to established Swedish and international guidelines. Patients with active or inactive (latent) tuberculosis cannot be included in the study.

The evaluation will include

- detailed medical history
- previous potential exposure for tuberculosis
- recent travel to countries with possible high exposure to tuberculosis
- previous and/or current immunosuppressive treatments
- pulmonary X-ray
- QuantiFeron[®] test

The investigator must be aware of the risk for a false negative tuberculin result in patients with serious disease or with impaired immune response.

Any indication of active or latent tuberculosis will exclude the patient from the study. These patients should be further investigated according to respective pediatric clinic's standard routines for tuberculosis diagnosis and excluded from enrollment in this study.

These patients cannot be enrolled in the study and cannot receive etanercept.

5.3.2 Screening for viral hepatitis, liver disease and renal insufficiency

All patients will be tested for Hepatitis B and C. Patients with prior or active hepatitis B and C will be excluded from the study.

All patients will, at the screening visit, be tested for liver disease (clinical and/or hepatic enzymes ≥ 3 times the upper limit of normal (ULN) and renal insufficiency (clinical and/or creatinine ≥ 3 times the upper limit of normal (ULN))

Patients with liver disease, renal insufficiency or tested positive for hepatitis B and/or C cannot be included in the study.

5.4 Patient Withdrawal

In accordance with the Declaration of Helsinki, the investigator must explain to the patient that they have the right to withdraw from the study at any time, and that this will in no way prejudice their future treatment. The reason for any kind of withdrawal must be recorded on the appropriate CRF.

There will be two main categories for withdrawals from the study:

Complete withdrawal (i.e. stopping investigational product and also continued efficacy and safety evaluations)

Standard reasons for withdrawing from further participation in the study and from the follow-up visits (and <e.g. blood tests>) may be:

- Patient's decision (withdrawal of consent to participate)
- Patient lost to follow-up

Withdrawals from investigational product (i.e. stopping one or several investigational products, but continuing follow-up visits, including efficacy and safety evaluations)

Standard reasons from withdrawing from taking further investigational product, but continuing follow-up visits and safety evaluations may be:

- Unacceptable adverse events
- Patient request
- Investigator's discretion
- Patient lost to follow-up/non-attendance
- Intercurrent illness
- The patient becomes pregnant

Thus subcutaneous GAD-Alum should not be given to the patient if the patient after inclusion in the study develops/experiences

- Brain damage, epilepsia, head trauma, neurological disease
- Any active, serious hormonal disease other than T1D
- Other severe autoimmune disease (except celiac disease which is accepted for inclusion.)
- Immune-suppressive treatment
- Cancer, cancer treatment
- Any other diabetes drugs other than insulin
- Any vaccination
- Drug/alcohol abuse
- Become pregnant or is no longer willing to use safe contraceptives during the study

Etanercept should not be continued if the patient after inclusion in the study develops/experiences

- Allergic reactions to etanercept or any of the excipients
- Other severe reactions to etanercept injections
- Sustained elevations of creatinine of liver function tests,
- Evidence of cardiac disorder
- Severe infections, such as sepsis, meningitis or osteomyelitis

- Suspected, latent or manifest tuberculosis
- Suspected or manifest viral hepatitis
- Severe lymphopenia
- Anemia
- Thrombocytopenia
- Malignancy
- Urticaria
- Varicella Zoster virus exposure or infection
- Live vaccines such as morbilli, parotitis, rubella, live polio, BCG and others
- Alcohol abuse or alcohol induced hepatitis
- Other autoimmune disease than T1D, such as SLE
- Pancytopeni or aplastic anemia (cautiousness should be taken with patients that have previously experienced blood dyscrasias).
- Become pregnant or is no longer willing to use safe contraceptives during the study
- Heart disease
- Impaired renal or liver function
- Neurological disturbances

Vitamin D treatment should not be continued if the patient after inclusion in the study develops/experiences

- Symptoms of hypercalcemia such as tiredness, euphoria, drowsiness, nausea, weight loss, thirst, polyuria, nefrocalcinosis, renal failure
- Arrhythmia
- Pancreatitis
- Vitamin D serum levels above 125 nmol/L.

However, whenever a patient is withdrawn from a study, or for whatever reason is not coming to any further visits, a final study evaluation must be completed for that patient (visit >) - stating the reason(s) why the patient was withdrawn from the study. All documentation concerning the patient must be as complete as possible.

Withdrawals due to non-attendance must be followed up by the investigator to obtain the reason for non-attendance. Withdrawals due to intercurrent illnesses or adverse events must be fully documented in the case report form, with the addition of supplementary information if available and/or appropriate.

6 Treatment Procedures

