6.7.1 General precautions during etanercept treatment (see Safety Plan for details)

To detect infections and other side effects as early as possible it is very important the investigator/study team cautiously collects symptoms and signs indicating any of the withdrawal criteria, as well as adverse events, and also be responsive to any spontaneous symptom/adverse event reporting in between study visits and at study visits. Patients who develop a new infection under etanercept treatment should be closely monitored. Fever is one of the first signs of infections.

The Medical Adviser will be contacted and the etanercept treatment will be interrupted, until a decision is taken by the responsible physician to continue or withdraw, if a patient during etanercept treatment develops or experiences

- Fever, long-lasting and/or low-grade
- Infection with fever

- Sore throat, especially with fever
- Fever with any kind of symptoms e.g. symptoms from a joint, red skin, difficulties to breath, abnormal tiredness
- Unexpected productive cough lasting two-three weeks or more
- Any abnormal signs such as pronounced tiredness, paleness, difficulties to breath, hematomas in the skin, bleedings, bruises, weight loss or any worrying symptom or sign
- Suspicion of exposure to tuberculosis or symptoms or signs of tuberculosis
- Suspicion of exposure to Varicella Zoster virus or symptoms or signs of chickenpox/shingles

All patients and their parent(s)/legal guardian(s) must be informed by the investigator and study team that they should seek medical help immediately in case the patient treated with etanercept develops signs and/or symptoms of blood dyscrasia or infections (long-lasting low-grade fever, sore throat, bruises, bleedings, weight loss, unexpected productive cough lasting two-three weeks or more and/or paleness).

Since fever is one of the first signs of infection, all patients and their parent(s)/legal guardian(s) will be informed to, during etanercept treatment, carefully follow the patient's general condition, and if affected, to measure the patient's morning body temperature daily, and in case it is elevated also measure it at least once more that day. The body temperature should be documented in the patient diary and the study team should be contacted.

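### Sections 5.4 and 6.7.1 give different dispositions for overlapping etanercept events: plainly for tuberculosis, more narrowly for varicella

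*Combined protocol and SAP*

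**What the plan says.** **Section 5.4 (Patient Withdrawal).** The etanercept list opens with "Etanercept should not be continued if the patient after inclusion in the study develops/experiences". Its entries include "Suspected, latent or manifest tuberculosis" and "Varicella Zoster virus exposure or infection". The list follows the category described as "Withdrawals from investigational product (i.e. stopping one or several investigational products, but continuing follow-up visits, including efficacy and safety evaluations". Section 5.4 does not say whether etanercept may be resumed later.

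**Section 6.7.1 (General precautions during etanercept treatment).** For a second list of events the Medical Adviser is contacted and "the etanercept treatment will be interrupted, until a decision is taken by the responsible physician to continue or withdraw". That list includes "Suspicion of exposure to tuberculosis or symptoms or signs of tuberculosis" and "Suspicion of exposure to Varicella Zoster virus or symptoms or signs of chickenpox/shingles". No condition is attached to continuing. The opening of 6.7.1 asks the team to look for symptoms and signs that point to any withdrawal criterion, and its heading refers to the Safety Plan for details.

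**Recording and populations.** Section 5.4 requires the reason for every withdrawal on the CRF. Section 10.4 requires a list of withdrawn patients with reasons and bases the per-protocol population on the absence of major violations, without defining major. The protocol has no rule for recording or tabulating an interruption that ends in resumption.

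**The concern.** Both sections apply to the same drug in the same period, and some clinical pictures meet a trigger in each. Section 5.4 then says etanercept should not go on, while 6.7.1 allows it to go on after a physician's decision. A site cannot tell from the protocol which section prevails.

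The events matter because they are named infection risks of a TNF blocker in children, and tolerability is the primary objective. Two patients with the same event could end with different etanercept exposure. One would appear as a withdrawal from product and the other would not appear at all. In a single-arm descriptive pilot of about 20 patients, meant to inform a larger Phase II trial, a reader needs to know how many children stopped etanercept and why.

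**Working it through.** There is no stated figure to reproduce. The check is a comparison of the two sections, followed by simple arithmetic for scale.

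**1. Triggers side by side**

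| Event | Section 5.4 | Section 6.7.1 | Same event under both? |
|---|---|---|---|
| Suspected exposure to tuberculosis | Not listed | Interrupt, then decide | No |
| Symptoms or signs of tuberculosis | Covered as suspected tuberculosis | Interrupt, then decide | Yes |
| Suspected exposure to varicella | Not listed; exposure is | Interrupt, then decide | Only once exposure is accepted as real |
| Signs of chickenpox/shingles | Overlaps with infection | Interrupt, then decide | Yes, where the signs reflect infection |

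**2. Can a staged reading remove the conflict?** The staged reading is to interrupt on suspicion under 6.7.1 and apply 5.4 on confirmation.
- For suspected exposure to either infection it works, because 5.4 does not list suspected exposure.
- For symptoms or signs of tuberculosis it does not work. They amount to suspicion, and 5.4 lists suspicion itself.
- For chickenpox/shingles it works only if someone decides whether the signs are an infection and 5.4 then governs. Section 6.7.1 does not say so.

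**3. Does 5.4 mean a permanent stop?** It does not say. Its vitamin D list uses the same lead-in and contains both levels above 125 nmol/L and symptoms of hypercalcemia. Section 6.7.2 restarts vitamin D once levels fall below 100 nmol/L, but rules out a restart after hypercalcemia. So the same wording covers a stop that can be reversed and one that cannot. For etanercept no section makes the distinction.

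**4. What changes in the data**
- Withdrawal list (10.4): a stop under 5.4 is a withdrawal from product with a reason. An interruption followed by resumption is not.
- Per-protocol population: a patient resumed under 6.7.1 has arguably departed from 5.4. Whether that is a major violation is undefined.
- Intention-to-treat population: it needs at least one dose of every study drug and a later assessment. An etanercept stop does not by itself change membership.
- Adverse events and infections: recorded whichever section is followed.

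**5. Scale, with the number of events assumed.** The documents give no event rate.
- Shift per patient: 1/20 = 5 percentage points.
- Exact 95% limits (Clopper-Pearson, n = 20) are the 0.025 quantile of Beta(x, n − x + 1) and the 0.975 quantile of Beta(x + 1, n − x), with lower limit 0 when x = 0. They give 0/20 = 0% (0 to 16.8%), 1/20 = 5% (0.1 to 24.9%) and 2/20 = 10% (1.2 to 31.7%).
- Exposure: weekly dosing on Days 1, 8, …, 85 is (85 − 1)/7 + 1 = 13 doses. Suppose an event falls after the fourth dose. A stop gives 4/13 = 31% of planned doses. Missing one dose and then resuming, with no dosing past Day 90, gives 12/13 = 92%.

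**The case against.** The strongest reply is that the sections are meant to work together. Section 6.7.1 presents itself as the means of detecting the withdrawal criteria, so the physician's choice may simply be the decision whether a 5.4 criterion is met. The Medical Adviser is contacted each time, which limits variation between sites. The Safety Plan was not available for this review and may settle the matter. Events should also be few: varicella immunity is required at entry, tuberculosis is screened for, and etanercept lasts 90 days.

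Much of this stands. The staged reading is partly supported and fits the suspected-exposure items. It does not reach symptoms or signs of tuberculosis, and the protocol nowhere says that 5.4 governs once 6.7.1 has been triggered. The Safety Plan is to be used with the protocol, but nothing in the protocol says that it overrides conflicting text. Required varicella immunity does not prevent exposure, which 5.4 lists.

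A reader might go further and infer that every tuberculosis or varicella trigger appears in both sections with opposite actions, or that the tolerability result as a whole depends on which section a site reads. The documents support neither. The triggers are not worded alike, and suspected exposure is not in 5.4. Infections and adverse events are recorded either way. No discontinuation rate is among the primary variables in 4.2.1 or the analyses in 10.3.

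**Conclusion.** The inconsistency is real but limited. It is clear for symptoms or signs of tuberculosis, and holds for signs of chickenpox/shingles so far as they reflect infection. Suspected exposure to either infection can be reconciled with 5.4 as a preliminary step. It would be tempting to read 5.4 as a permanent stop that 6.7.1 flatly overturns, but the protocol's own use of the same wording for vitamin D does not bear that out.

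The consequences are the handling of a safety event in a child, the etanercept exposure that follows, the list of withdrawals from product, and possibly per-protocol membership. The 5 points per patient and the dose illustration show scale only. They assume that such an event occurs, and the first describes a proportion that the plan does not define. The conclusion also assumes that the Safety Plan does not already resolve the overlap. With no hypothesis test in the plan, no inferential result is at risk. The point merits correction because it is safety-relevant and cheap to fix.

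**What to change.** The sponsor should reconcile 5.4 and 6.7.1 and check both against the Safety Plan:
- Use the same terms in each place for suspicion, exposure and confirmed infection, separately for tuberculosis and varicella.
- State how an interruption under 6.7.1 leads to a decision under 5.4, and which section governs when both apply.
- State whether an etanercept stop under 5.4 is permanent.
- Report temporary interruptions and permanent stops of etanercept separately in the tolerability summary, with reasons.

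The sponsor decides the clinical rule, including whether it is staged. This review takes no position on that.

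The cost is wording in two sections and one extra table line, plus a CRF field if the CRF does not already separate interruption from stop. No further visits, samples or patients are needed.
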